1.1 Previous Clinical Experience

1.1.1 Phase 1

Study C3J11-101-01, a Phase 1, randomized, double-blind, placebo-controlled, dose escalation study was conducted at a single study center in the US. A total of 36 healthy adult subjects were enrolled, of which 24 subjects received C16G2, and 12 subjects received placebo. C16G2 was administered in a mouth rinse formulation as a single dose of three concentrations (4 mg [50 μ M], 8 mg [100 μ M] and 32 mg [400 μ M]) by swishing for 40 seconds in the oral cavity and subsequent expectoration.

The objectives of this study were to evaluate the safety and pharmacokinetics of C16G2 in healthy adult subjects and to assess the targeted antimicrobial activity of C16G2 as measured by a

reduction in the number of salivary *S. mutans* and to assess the bacterial composition in the oral cavity over 28 days post-study drug administration in healthy adult subjects.

C16G2 was well-tolerated with no deaths and no other serious or severe AEs. No study drug-related treatment-emergent AEs were reported and no subject was discontinued due to an AE. No clinically significant changes in vital signs were observed in association with the administration of C16G2. Mean values for systolic and diastolic blood pressure and pulse showed only small fluctuations from baseline over the entire treatment period, and values were similar for the C16G2 dose cohorts and the placebo cohort. No clinically significant findings in the oral cavity were attributable to C16G2 administration and no clinically significant targeted physical exam and electrocardiogram (ECG) findings were reported. In addition, no clinically significant out-of-range clinical laboratory findings were observed. Immunogenicity assessments demonstrated that single dose C16G2 administrations up to a dose of 32 mg did not trigger the development of antibodies against C16G2.

C16G2 could not be detected above the lower level of quantitation (LLOQ 10ng/mL) in any pharmacokinetic sample, with a single exception, which tested just above the LLOQ and was most likely the result of high background signal near the LLOQ. This suggests that there is minimal or no systemic absorption of C16G2 into the circulation after a single C16G2 administration up to a dose of 32 mg.

Microbiology assessments did not demonstrate an apparent reduction or increase in *S. mutans* and other bacterial species outside of the variation observed in the placebo cohort, indicating that single C16G2 doses formulated as a mouth rinse did not impact the oral microbiome.

Study C3J16-V102-00, a Phase 1, single-blind, randomized, placebo-controlled, dose-escalation study evaluated the safety and efficacy of single 13.6 mg, 27.2 mg, 54.4 mg C16G2 Varnish or Placebo administrations.

The objectives of this study were to evaluate the safety and microbiology of C16G2 Varnish formulation in healthy adult subjects and to assess the targeted antimicrobial activity of C16G2 as measured by a reduction in the number of salivary *S. mutans*. In addition, the study assessed the bacterial composition in the oral cavity over 28 days post single study drug administration in healthy adult dental subjects.

A total of 48 adult healthy subjects were enrolled, of which 30 subjects received C16G2 and 18 subjects received placebo. C16G2 was well-tolerated with no deaths and no other serious or severe AEs. No study drug-related treatment-emergent AEs were reported and no subject was discontinued due to an AE. No clinically significant changes in vital signs were observed in association with the administration of C16G2. Oral cavity assessments and targeted physical exams did not indicate any clinically relevant changes due to study drug administration. Microbiology evaluations demonstrated a significant decrease in *S. mutans* levels in saliva and plaque samples in each dose level. The 27.2 mg dose group showed the greatest decrease in *S. mutans* compared to Placebo and the other two dose groups. Total bacteria levels did not change significantly post study drug administration. The clinical study report for this study is currently in preparation.

1.1.2 Phase 2

To enhance the targeted *S. mutans* killing activity of C16G2 in dental plaque, C3 Jian formulated the drug product for both mouth rinse and gel application. C3J13-201-01, a double-blind, placebo-

controlled study, evaluated different combinations of multiple C16G2 Gel and/or C16G2 mouth rinse administrations at two dose levels. To determine the most effective mode of gel application, gel was applied by manual toothbrush, Sonicare™ toothbrush and upper and lower custom dental trays.

Clinically significant findings in the oral cavity and targeted physical exam were reported as adverse events. No clinically significant changes in vital signs were observed in association with administration of C16G2. Mean values for systolic and diastolic blood pressure, pulse and temperature showed only small fluctuations from baseline over the entire treatment period, and values were similar for the four active C16G2 Study Arm groups and combined placebo group.

The majority of subjects receiving C16G2 via a custom dental tray demonstrated an average 1 \log_{10} CFU/mL *S. mutans* reduction in saliva 1 day after the last 7-day study drug administration period and this reduction was maintained in some subjects 1 week after the last study drug administration, demonstrating the durability of effect for 7 days. The majority of subjects receiving C16G2 Gel via a manual toothbrush demonstrated an *S. mutans* reduction in occlusal dental plaque 1 day after the last 7-day study drug administration period, with fewer subjects having an impact in salivary *S. mutans*. At the end of the study, only a portion of subjects in the manual brush arm showed a substantial reduction in *S. mutans* occlusal dental plaque and the effect was less pronounced in saliva, indicating that the response observed on Day 7 may decrease over time post-treatment. Other modes of application (mouth rinse, gel administered via Sonicare™ toothbrush) were less effective.

In the open-label study C3J14-201B-00, subjects received 400 μ M and 800 μ M C16G2 Gel, administered either by custom dental trays once daily for 5 consecutive days (Part A) or via manual toothbrush only compared to a combination of manual toothbrush and custom dental trays

(Part B), with four study drug administrations on the first day of dosing followed by AM and PM dosing for 6 consecutive days. Results from Part A of the study demonstrated that C16G2 administered once daily for 5 days via dental trays for up to 4 hours did not suppress *S. mutans* efficiently. Results from Part B of the study showed a $1 \log_{10}$ CFU/mL suppression of *S. mutans* when C16G2 was applied via a manual toothbrush and custom dental tray combination and at the higher concentration (800 μ M).

Pharmacokinetic data from study C3J14-201B-00 indicated no detectable systemic levels of C16G2 (all samples below the LLOQ of 10 ng/mL). PK samples were obtained: 1) during and after a 4 hour gel tray administration of 3.2 mg/mL C16G2 in gel (C16G2 administered after manual brushing with conventional toothpaste without C16G2), and 2) immediately after 3 manual brushings with C16G2 and one 30 minute tray administration with C16G2 (3.2 mg/mL C16G2 in gel).

Study C3J15-202-00, a Phase 2, multi-center, randomized, double-blind, placebo-controlled study evaluated the safety and microbiology of C16G2 (gel formulation) in adolescent and adult dental subjects. The study evaluated the treatment regimen and schedule previously assessed in Study C3J14-201B-00, Part B and assessed the durability of *S. mutans* suppression over a longer period of time (up to 4 months compared to 7 days in previous studies), evaluated the safety and microbiology of two 7-day study drug administration periods, and compared 2 mL (Study Arm 1) versus 4 mL (Study Arm 2) 800 μ M C16G2 Gel/Placebo administrations.

A total of 64 subjects were enrolled into this study, of which 41 were randomized to receive active drug. A total of 104 AEs were reported in 36 subjects, with a similar distribution over the two study arms and the placebo group (Study Arm 1: 9 subjects; Study Arm 2: 16 subjects; placebo group: 11 subjects). AEs related to study drug were reported for 3 subjects receiving C16G2 (all in Study Arm 2) and 2 subjects treated with placebo. AEs deemed related to the study drug in Study Arm 2 were gingival swelling, oral discomfort, and sensitivity of teeth, all assessed as mild in severity. There were no serious adverse experiences (SAEs) or severe AEs, no deaths, and no discontinuations due to AEs.

No clinically significant changes in vital signs were observed in association with administration of C16G2. Assessments of the oral cavity and body areas examined as part of the targeted physical exams did not reveal any treatment-related safety issues. Thus, the dosing regimens and modes of application evaluated in this study were safe in healthy adults and adolescents.

Results for salivary *S. mutans* samples during the first and second study drug administration period suggest that either 2 or 4 mL volumes of 800 μ M C16G2 delivered via MBGA and TGA over 7 days, with an intensive first day, are sufficient to suppress *S. mutans* for 12 hours following the cessation of therapy compared to placebo.

Results for occlusal dental plaque during the first study drug administration period suggest that 800 μ M C16G2 administered as either 2 or 4 mL volumes via MBGA and TGA over 7 days, with an intensive first day, are sufficient to suppress *S. mutans* in dental plaque for up to 12 hours after the last dose as compared to placebo. During the second study drug administration only the 4 mL volume appeared sufficient to suppress *S. mutans* up to 12 hours in both plaque and saliva, while 2 mL suppressed *S. mutans* in saliva.

In both study drug administration periods total bacterial loads were not reduced by study treatments at 1 week post last study drug administration. The magnitude of the *S. mutans* reduction in the first study drug administration period was modest, yet selective, since there was no change in total bacterial levels.

Study C3J15-203-00, a Phase 2, multi-center, randomized, double-blind and open-label, placebo-controlled study evaluated the safety and microbiology of C16G2 administered in multiple oral gel

doses to adult and adolescent dental subjects. The study evaluated different dosing regimens and different doses of C16G2 and Placebo. There were no significant safety findings and the safety profile of C16G2 was consistent with previous studies and generally safe in the majority of subjects. Microbiology results did not show a significant durable response in the reduction of *S. mutans* in stimulated saliva and dental plaque samples. Total bacteria levels did not change significantly post study drug administration. Application of C16G2 (800 μ M & 1600 μ M) with twice daily tray on a single day provided a significant reduction in *S. mutans* although that level of reduction was not sustained with subsequent applications performed with a combination of brush and tray. The clinical study report for this study is currently in preparation.

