	
oral hygiene in the morning at home. In addition, subjects will be advised not to use any mouth rinse for approximately 24 hours before the Screening visit.
 
Prior to discharge at Visit 2/Day -7 to -2, subjects will receive a manual toothbrush, a regular toothpaste containing fluoride (e.g., Crest Regular™), and dental floss provided by the Sponsor to take home. Subjects will be instructed to use these dental products in the morning and evening at home during the remaining study duration, including the evenings of days of study drug administration (Visits 3-5). In addition, subjects will be resupplied with these dental products as needed.
 
b) Diet Instructions
 
Subjects will be instructed as follows:
 
All Visits:
 
 • Do not eat for 1 hour prior to the appointment time • No liquids, other than plain water, 1 hour prior to the appointment time 
Note: Subjects will be allowed to drink plain water up to 10 minutes prior to dental plaque and saliva collection, and will be instructed not to swish or rinse
 
Visits 3-5
 
 • Do not eat, drink anything except plain water or swish from the start of study drug administration to 1 hour after the study drug application
Safety Monitoring:	
All subjects that receive study drug will be included in the safety analysis. Safety will be evaluated on the entire study population of up to 33 subjects. Subjects will be followed for safety assessments for 1 week after the last study drug administration. Safety monitoring will include vital signs, intraoral assessments of hard and soft tissues, targeted physical examination, and collection of adverse events during study visits and unscheduled telephone contacts.
 
Subjects will be instructed to inform the Investigator and/or a member of the study staff of any adverse events that occur at any time during the study. Subjects will be asked a general health question at each clinic visit up to and including Visit 8 and with each unscheduled telephone contact to identify changes in their state of health since their last communication with the study center or their last study visit. All subjects will be closely monitored for safety for 1 week after administration of study drug. After that time point, all ongoing adverse events will be followed in accordance with good medical practice until resolution or the condition has stabilized.

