8.7.5 Safety Analysis

8.7.6.1 Adverse Events

Adverse events (AE) will be classified into standard terminology (preferred term and system organ class) using the Medical Dictionary for Regulatory Activities. The severity of each adverse event will be graded as 1) mild, 2) moderate, 3) severe, or 4) life-threatening, according to the Common Terminology Criteria for Adverse Events (CTCAE) version 4.0.

In addition, all adverse events will be classified as to whether the relationship to study drug was 1) None, 2) Unlikely, 3) Possible, or 4) Probable and followed to resolution or until the adverse event or condition has stabilized.

The incidence and duration of treatment-emergent adverse events (TEAEs) will be summarized by treatment group according to MedDRA-preferred term and MedDRA system organ class term. An AE will be considered treatment emergent if the onset date and time occur on or after the recorded clock time of study drug administration. Tabulations of adverse events by severity grade and causal relationship to study drug (related, unrelated) will be provided.

For reporting purposes, AEs assigned a relationship to study drug of "Possible" and "Probable" will be classified as related to study drug. AEs assigned a relationship to study drug of "Unlikely" or "None" will be classified as not related to study drug.

The number and percentage of subjects with reported serious adverse experiences (SAEs) and subjects who withdrew due to an AE will be tabulated by treatment group.

All adverse events will be presented in by-subject listings by reported verbatim term and MedDRA-preferred term, MedDRA system organ class, start and stop date and time, study day, duration, severity, relationship to study drug, seriousness, and outcome. All reported serious adverse events will also be displayed in by-subject listings.

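### Oral discomfort and tooth sensitivity are sought only by a general health question and spontaneous report, although tolerability is part of the primary objective

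*Combined protocol and SAP*

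**What the plan says.** Section 2 makes safety and tolerability of repeated varnish application the primary objective. Section 5 plans 8 active and 3 placebo subjects at each of up to three doses.

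Section 1.1.2 describes Study C3J15-202-00, a gel study with a 2 mL arm (Arm 1) and a 4 mL arm (Arm 2). It reports that "A total of 64 subjects were enrolled into this study, of which 41 were randomized to receive active drug", that "AEs related to study drug were reported for 3 subjects receiving C16G2 (all in Study Arm 2) and 2 subjects treated with placebo", and that "AEs deemed related to the study drug in Study Arm 2 were gingival swelling, oral discomfort, and sensitivity of teeth". All three were mild.

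The present trial collects local effects by these routes:

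- **Questioning.** Synopsis, Safety Monitoring: "Subjects will be asked a general health question at each clinic visit up to and including Visit 8", and at unscheduled telephone contacts. Subjects are also told to report any event, and Appendix B (footnote k) adds a reminder until Visit 8.
- **Examination.** Section 1.5.4 describes a hard-tissue check with a dental mirror and a soft-tissue check, gingiva included, by sight and touch. Under Section 6.3.2 and Appendix B (footnote m) it is done before and after each application at Visits 3 to 5, and again at Visits 6 and 8. Visit 7 has adverse event collection but no oral examination.
- **Tabulation.** Under Section 8.7.6.1, treatment-emergent events are "summarized by treatment group according to MedDRA-preferred term and MedDRA system organ class term", with tables by severity and relatedness and full listings. Section 8.7.6.2 counts subjects with clinically significant oral cavity findings.

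**The concern.** Two of the three event types that the protocol itself records as drug-related are felt by the subject and cannot be seen by the examiner. No symptom list, scale or diary appears in the protocol. The Study Manual is cited but is not among the documents, so it could hold a script that cannot be checked here.

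At stake is the primary question. A mild ache or sensitivity may not come to mind when a subject is asked about general health. With 8 active subjects per dose, one or two unreported cases can turn a dose with local symptoms into one that shows none. In the tables, discomfort, sensitivity and swelling would fall under separate preferred terms, and the Section 8.7.6.2 count takes only examination findings. No row counts the subjects with any local oral reaction at each dose.

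**Working it through.** **1. Reproduce the stated figures.** Subjects with any adverse event in the gel study: 9 + 16 + 11 = 36, as stated. Placebo subjects: 64 − 41 = 23. This trial: 3 × (8 + 3) = 33, as stated. The protocol sets no power, effect size or symptom rate, so there is no further figure to reproduce.

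**2. Is there a drug signal in the gel study?** Exact (Clopper-Pearson) 95% intervals for subjects with a related event:

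- Active: 3/41 = 7.3% (1.5% to 19.9%).
- Placebo: 2/23 = 8.7% (1.1% to 28.0%).
- Fisher's exact p = 1.0.

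Arm sizes are not given. Arm 2 had at least 16 subjects, because 16 had an event, and at most 41 − 9 = 32, because 9 in Arm 1 had one. Its related-event rate therefore lies between 3/32 = 9.4% and 3/16 = 18.8%. Against placebo, Fisher's p is 1.0 at 32 subjects and 0.63 at 16. No excess is shown, and the numbers are too small to exclude one.

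**3. Which route can find each event type?**

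| Event type | Oral examination | General question or volunteered |
|---|---|---|
| Gingival swelling | Yes (gingiva inspected and palpated) | Yes |
| Oral discomfort | No | Yes |
| Tooth sensitivity | No symptom item described | Yes |

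Even for swelling the examination may not be complete. Section 1.1.2 says the examinations in the gel study showed no treatment-related problem, yet gingival swelling was recorded there as a related event.

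**4. Illustration of what incomplete capture could do.** Let p be the true rate, s the share captured and n the number of subjects. Then P(at least one reported case) = 1 − (1 − p·s)^n. Both p and s are assumptions. The range for p is borrowed from step 2, from 3/41 (all active) to 3/16 (smallest possible Arm 2), with 3/20 = 15% as a middle value under an assumed near-even split. These rates cover any related event; rates for discomfort and sensitivity alone are not given.

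| p | s | n = 8 | n = 24 |
|---|---|---|---|
| 3/41 | 1 | 46% | 84% |
| 3/41 | 0.5 | 26% | 59% |
| 3/20 | 1 | 73% | 98% |
| 3/20 | 0.5 | 46% | 85% |
| 3/16 | 1 | 81% | 99% |
| 3/16 | 0.5 | 55% | 91% |

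For example, at p = 0.15 and s = 0.5 with n = 8: 1 − 0.925^8 = 0.46. The n = 24 column applies only if all three cohorts enrol.

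**5. How much can 8 subjects exclude?** With perfect capture, 0/8 has an exact 95% upper limit of 1 − 0.025^(1/8) = 37%. There is little room for missed reports.

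**The case against.** The strongest objection is the varnish evidence. Study C3J16-V102-00 (Sections 1.1.1 and 1.6) applied the same three varnish doses once. It saw no related treatment-emergent events in 30 active subjects, and only two adverse events, both judged unrelated. For 0/30 the exact 95% upper limit is 1 − 0.025^(1/30) = 11.6%, so high symptom rates look unlikely. This stands and lowers the priority of the point. It does not close it, because V102 was single-dose, repeated application is what this trial adds, and the protocol does not say how V102 elicited symptoms.

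Three stronger readings are tempting, and the documents do not support them:

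- **That adverse events are sought by one question alone.** They are not. Oral examinations are scheduled around every application and in follow-up, gingival swelling is actively looked for, and subjects are reminded to report.
- **That the gel study shows a volume-related drug effect, because every active case was in the 4 mL arm.** Two placebo subjects also had related events, of unstated type, and step 2 shows no excess.
- **That the gel study's any-event counts (9, 16 and 11 subjects) are wrongly described as reported "with a similar distribution over the two study arms and the placebo group".** Without arm sizes this cannot be judged. It is background text about another study and changes nothing in this trial's analysis.

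It can also be said that with at most 33 subjects a reader could count local reactions from the listings. That is true, but listings recover only what was reported.

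**Conclusion.** The point holds in a limited form. Oral discomfort and tooth sensitivity have no solicited assessment in a trial whose primary objective includes tolerability, and the scheduled examinations cannot supply one. Mild local symptoms may be under-reported.

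How many would be missed cannot be computed, since neither the true rate under repeated varnish nor the share captured by a general question is in the documents. The figures in step 4 show direction and rough scale under stated assumptions only. The point does not rest on a demonstrated harm: the gel study shows no excess over placebo, and the single-dose varnish study shows no related events. This is a worthwhile low-cost improvement, not a proven error.

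**What to change.** 1. After the general health question, ask every subject the same scripted yes/no items on mouth discomfort, tooth sensitivity and gum swelling. Ask them before the first application at Visit 3 and at each adverse event query through Visit 8.
2. Record as an adverse event only a symptom that is new or worse than the pre-dose answer, in line with Section 7.1. Without the pre-dose question, existing sensitivity would be counted as treatment-emergent.
3. Flag each report as prompted or unprompted, so that the unprompted count is kept.
4. In Section 8.7.6.1 add one row: subjects with any new or worsened local oral reaction (these symptoms or oral examination findings), by dose and for placebo, with exact 95% confidence intervals.

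**Cost.** Three items at one pre-dose and six later queries (Visits 3 to 8) make 3 × 7 = 21 short answers per subject, plus one table row. Prompting will raise counts in all groups, placebo included, and make rates less comparable with earlier studies. The flag helps, but subjects who have once been asked may volunteer more at later visits. Site staff know the allocation (Sections 3.1.2 and 8.3), so the answers are taken by unblinded people. A fixed script limits that risk but does not remove it.
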